7.4.6.6 Response Rate per the Proposed Revised IWG Response Criteria

The following response rate analyses will be performed based on the mITT analysis set:

• CR/CR with partial hematologic recovery (CR_h) Rate

 CR/CR_h is defined as achievement of CR or CR_h as determined by the proposed revised IWG MDS criteria (Zeidan 2023, Appendix 2).

The number and percentage of participants achieving CR or CR_h and 95% exact binomial CIs based on the Clopper-Pearson exact method will be calculated and summarized by treatment group.

• CR/PR/CR_h Rate

CR/PR/CR_h is defined as achievement of CR, PR, or CR_h as determined by the proposed revised IWG MDS criteria (Zeidan 2023, Appendix 2). The number and percentage of participants achieving CR, PR, or CR_h and 95% exact binomial CIs based on the Clopper-Pearson exact method will be calculated and summarized by treatment group.

7.4.6.7 Transfusion Rate

Participants who have been on treatment for at least 56 days are considered evaluable for this analysis.

Definitions:

• Baseline Transfusion Dependence:

Transfusion of ≥ 1 unit of RBCs and/or platelets during the 56 days prior to date of randomization.

• Baseline TI:

No RBC or platelet transfusions during the 56 days prior to date of randomization.

• Post-baseline TI:

Post-baseline TI is defined as a period of at least 56 days with no RBC or platelet transfusion since the date of randomization to the last dose of study drug + 30 days, the initiation of post-treatment therapy, or death, whichever occurs first.

Analyses:

The mITT Analysis Set will be used for the following transfusion rate analyses.

Overall transfusion status (RBC or platelets), RBC transfusion status, and platelet transfusion status will be analyzed separately as below:

• Rate of conversion of baseline transfusion dependence to post-baseline TI in the baseline transfusion-dependent mITT participants.

The number and percentage of mITT participants who are transfusion dependent at baseline and the number and percentage of baseline transfusion-dependent mITT participants who achieved post-baseline TI, along with respective 95% exact binomial CIs, will be summarized by treatment group.

• Rate of maintenance of baseline TI in the baseline transfusion-independent mITT patients.

The number and percentage of mITT participants who are transfusion independent at baseline and the number and percentage of baseline transfusion-independent mITT participants who maintained TI post-baseline will be summarized by treatment group.

In addition, the median number of units of RBC and platelets received in 56 days blocks (e.g., Day 1 to Day 56, Day 57 to Day 112, and etc.) starting from Cycle 1 Day 1 will be reported for each treatment group.

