6.4.1.3 Secondary Efficacy Endpoints and Estimands

The secondary efficacy endpoints are:

• TI, defined as a period of at least 56 days with no red blood cell (RBC) or platelet transfusion since the date of randomization to the last dose of study drug + 30 days, the initiation of post-treatment therapy, or death, whichever occurs first. TI rate is calculated as:

TI rate (%) = number of participants who achieve TI / number of participants in the mITT analysis set \times 100. The denominator is the mITT population in each treatment group.

• Overall response, defined as achieving CR, partial remission (PR), marrow CR (mCR), or subcategories of hematologic improvement (HI), as determined by the investigator per the modified IWG MDS criteria (Cheson 2006). ORR will be calculated as:

ORR (%) = number of overall responders / number of participants in the mITT analysis set \times 100. The denominator is the mITT population in each treatment group.

Overall response may also be analyzed in line with the updated IWG response criteria (Zeidan 2023).

• DOCR, defined as the duration from the date of first documented evidence of CR to the date of documented relapse of disease or disease progression, as determined by the investigator per the modified IWG MDS criteria (Cheson 2006), or death due to any cause, whichever occurs first. Among CR responders, DOCR will be calculated in months as:

DOCR (months) = (first date of documented relapse of disease, disease progression, or death due to any cause - date of first documented evidence of <math>CR + 1) / 30.4375.

• Duration of overall response, defined as the duration from the date of first documented evidence of CR, PR, mCR, or HI, to the date of documented disease progression or relapse of disease, as determined by the investigator per the modified IWG MDS criteria (Cheson 2006), or death due to any cause, whichever occurs first. Among overall responders, duration of overall response will be calculated in months as:

Duration of overall response (months) = (first date of documented disease progression, relapse of disease, or death due to any cause - date of first documented evidence of CR, PR, mCR, or HI + 1) / 30.4375.

• Time to CR, defined as the duration from the date of randomization to the date of the first documented evidence of CR as determined by the investigator per the modified IWG MDS criteria (Cheson 2006). Among CR responders, this endpoint will be calculated as:

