7.2 Analysis Sets

7.2.1 Modified Intent-to-Treat Analysis Set

The mITT Analysis Set includes the first approximately **CCI** randomized participants. Treatment groups and stratification for this analysis set will be determined according to the treatment and stratification assignments at the time of randomization.

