7.4.5 Secondary Efficacy Endpoints Analysis Methods

7.4.5.1 Transfusion Independence

TI is defined as a period of at least 56 days with no RBC or platelet transfusion since the date of randomization to the last dose of study drug + 30 days, the initiation of posttreatment therapy, or death, whichever occurs first. The overall TI rate (based on receiving neither RBC nor platelet transfusion for post-baseline period of any at least 56 days) with respective 95% exact binomial CIs based on the Clopper-Pearson exact method will be calculated by treatment group. The stratified CMH test will be applied to compare the TI rates between the 2 treatment groups. The RBC TI rate and the platelet TI rate, along with 95% exact binomial CIs, will also be calculated and summarized by treatment group. Analyses of the TI rates will be based on the mITT analysis set.

A by-participant listing of the derived efficacy data used for determining the TI rate will be provided.

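### The 56-day treatment condition on the exploratory transfusion conversion and maintenance rates is a post-randomisation selection that does not fit the stated mITT denominators

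*SAP*

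**What the plan says.** SAP 7.4.6.7 (Transfusion Rate) begins with an evaluability rule: "Participants who have been on treatment for at least 56 days are considered evaluable for this analysis". Further down, the same section says: "The mITT Analysis Set will be used for the following transfusion rate analyses". It then names two rates, each with its own denominator and no condition on treatment duration:

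- "Rate of conversion of baseline transfusion dependence to post-baseline TI in the baseline transfusion-dependent mITT participants"
- "Rate of maintenance of baseline TI in the baseline transfusion-independent mITT patients"

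Post-baseline TI in that section needs at least 56 transfusion-free days in a window that starts at randomisation and runs "to the last dose of study drug + 30 days, the initiation of post-treatment therapy, or death, whichever occurs first".

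The mITT set in SAP 7.2.1 is a count of the first randomised participants, with no treatment-duration condition: "Treatment groups and stratification for this analysis set will be determined according to the treatment and stratification assignments at the time of randomization". For the secondary TI rate, SAP 6.4.1.3 states: "The denominator is the mITT population in each treatment group". SAP 7.4.5.1 repeats it: "Analyses of the TI rates will be based on the mITT analysis set". SAP Table 5 handles death, withdrawal of consent or new anticancer therapy before a response by a composite strategy. None of the analysis sets in SAP 7.2 is an evaluable mITT subset.

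**The concern.** Whether a participant stays on treatment for 56 days depends on death, toxicity, progression and withdrawal, and treatment can affect each of these. A denominator limited to those who reach day 56 is therefore no longer the randomised comparison. If more participants stop early in one arm, the two denominators shrink by different proportions, and the by-arm rates can differ for that reason alone.

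There are two further problems. The section does not say how the 56-day rule combines with its own mITT wording, so two programmers could produce different tables. The rule also does not match the TI definition it serves, because someone treated for less than 56 days can still have a qualifying 56-day period.

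The stake is modest but real. The secondary TI rate pools participants who were transfusion dependent and independent at baseline. This section is where conversion and maintenance are separated.

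**Working it through.** The documents give no planned rate, power or sample size for this analysis, so there is no stated figure to reproduce.

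**1. Which denominator?** The evaluability sentence requires at least 56 days on treatment. The mITT sentence and both rate descriptions carry no such requirement. The secondary TI rate, which uses the same TI definition, has the full mITT as its denominator. Applied literally, the 56-day rule would stop the 7.4.6.7 counts from summing to the secondary TI counts.

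**2. Does the rule match the TI definition?** Let D be the day of last dose, counting randomisation as day 1. The window ends at D + 30 unless death or post-treatment therapy comes first. A 56-day period fits if D + 30 ≥ 56, that is, D ≥ 26. As an example, a participant who completes one cycle on the standard schedule has a last tamibarotene/placebo dose on Day 28, and the window ends on day 28 + 30 = 58. Participants treated for about 26 to 55 days can therefore meet the SAP definition and still be non-evaluable. (It is *about* 26 because randomisation may precede the first dose by up to 72 hours.)

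**3. How far can the rates move?** Let p be the conversion rate in all baseline-dependent mITT participants of an arm, d the share of them treated for less than 56 days, and r the TI rate among those excluded. Then:

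restricted rate = (p − d·r) / (1 − d)

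The values of p, d and r below are assumptions. Setting r = 0 reduces the formula to p / (1 − d). With p = 0.40 in both arms, so that the mITT difference is zero:

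| Early stopping, tamibarotene vs placebo | Restricted rates | Difference (points) |
|---|---|---|
| 15% vs 8% | 0.40/0.85 = 47.1% vs 0.40/0.92 = 43.5% | +3.6 |
| 20% vs 10% | 0.40/0.80 = 50.0% vs 0.40/0.90 = 44.4% | +5.6 |
| 10% vs 10% | 44.4% vs 44.4% | 0, both rates inflated |
| 10% vs 20% | 44.4% vs 50.0% | −5.6 |

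Varying p from 0.30 to 0.50 gives +2.0 to +3.3 points for early stopping of 15% vs 10%, +4.2 to +6.9 for 20% vs 10%, and +6.7 to +11.1 for 25% vs 10%.

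**4. The role of r.** Participants whose last dose falls before day 26 must have r = 0. Those treated for about 26 to 55 days need not. With p = 0.40 and d = 0.20, r = 0.20 gives (0.40 − 0.04)/0.80 = 45.0%, not 50.0%. If r = p the restriction changes nothing, and if r > p it lowers the rate.

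**5. Scale in patients.** Protocol 9.4.2 gives 190 patients for the CR analysis. SAP 7.4.7.1 agrees, with the 95th participant at information fraction 0.5 (95/0.5 = 190). Taking 190 as the approximate mITT size, 2:1 allocation gives about 127 and 63. Assuming half are baseline dependent gives about 64 and 32.

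- Full denominators: 26/64 = 40.6% vs 13/32 = 40.6%, difference 0.
- After excluding 20% (13) and 10% (3): 26/51 = 51.0% vs 13/29 = 44.8%, difference +6.2 points.
- For comparison, the 95% half-width for a difference at 40% is 1.96 × √[0.24 × (1/64 + 1/32)] = 0.208, about 21 points.

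**The case against.** The mITT sentence can be read as naming the parent set, with evaluability applied inside it. The SAP uses mITT subsets elsewhere: cytogenetic CR is limited to mITT participants with a baseline chromosomal abnormality. On that reading a flat contradiction, which a reader might infer, is more than the text supports; the denominator is undetermined. That part of the objection stands. It does not rescue the rule, because the cytogenetic subset is fixed at baseline while this one depends on treatment duration after randomisation.

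The analysis is also exploratory and descriptive. SAP 7.4.6.7 asks for summaries by arm, with exact confidence intervals specified for conversion only, and names no between-arm test. The unfiltered TI comparison is already planned as a secondary analysis, with a stratified CMH test. Any plausible shift is small against the sampling error in step 5. All of this stands and keeps the priority low. However, full-mITT rates by baseline transfusion status are not planned elsewhere, so the secondary analysis does not fill the gap.

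For maintenance, scoring a baseline-independent participant who stops very early without a transfusion as not maintained is a convention. An evaluable subset is another. That is fair, and it is a reason to show the number of short-treated participants by arm.

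**Conclusion.** The point holds at low priority. The 56-day condition selects on a post-randomisation outcome, does not fit the denominators stated beside it, and can remove participants who meet the SAP's own TI definition.

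The size is illustrative: +3.6 points for early stopping of 15% vs 8% and +5.6 for 20% vs 10%. Both figures assume 40% mITT conversion in each arm and no TI among those excluded. Equal stopping gives no difference but raises both rates, and reversed stopping reverses the sign.

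Three stronger readings are tempting and should not be drawn:

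- **That the rule favours tamibarotene, or always favours the arm with more early stopping.** The documents give no early-stopping rates by arm, and the upward shift depends on those excluded having a lower TI rate than their arm as a whole.
- **That every early stop should count as a failure.** That would misclassify participants treated for about 26 to 55 days who have a qualifying transfusion-free period.
- **That the trial's main conclusions are exposed.** Primary CR, key secondary OS and the secondary TI rate do not use this filter, and the SAP gives the 7.4.6.7 rates no formal role in interpreting secondary TI.

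**What to change.** In SAP 7.4.6.7:

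1. Delete the 56-day evaluability sentence, or keep that subset only as a summary labelled supplementary. If it is kept, define time on treatment, because SAP 7.3.10 calculates exposure separately for each drug.
2. Use all baseline transfusion-dependent mITT participants as the denominator for conversion, and all baseline transfusion-independent mITT participants for maintenance.
3. Score post-baseline TI by the definition already in the section. Early stoppers then count as not achieving TI unless they have a qualifying 56-day transfusion-free period.
4. Report by arm the number treated for less than 56 days.

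The cost is a short SAP edit with no new data collection. The reported rates may be slightly lower.

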7.4.6.8 Sensitivity Analysis for Selecting RARA Overexpression

A sensitivity analysis will be performed to explore the cutoff values of delta Cq used in the RARA biomarker assay for selecting for responses for participants in the mITT Analysis Set. A logistic regression model with CR (responder vs non-responder) as the binary dependent variable and treatment group, delta Cq, and interaction between treatment group and delta Cq as covariates will be used to find the delta Cq cutoff value that optimally selects for the response from the receiver operating characteristic (ROC) curve. First, test if there is interaction between the treatment group and delta Cq by using the Wald Chi-Square test. If no interaction is found, the interaction term (treatment group \times delta Cq) will be removed from the model, and only treatment group and delta Cq will be kept in the model as covariates. If there is an interaction, further investigation must be performed to qualitatively characterize the differences in RARA overexpression.

The steps to finding the best delta Cq cutoff value are as follows:

Step 1: Use PROC LOGISTIC in SAS with the CTABLE option in the model statement to display a table with statistics for each range of cut points, including true positive percentage and true negative percentage.

Proc logistic data=xx;

Class treatment;

Model response (Event = '1') = delta_Cq treatment/ctable;

Run;

Step 2: Calculate Youden's J statistic as

J = true positive percentage + true negative percentage - 100.

Step 3: Obtain the Max (J) and find the corresponding probability level.

Step 4: Use the fitted logit equation from SAS output:

Logit (probability level) = Intercept + $B \times delta Cq + C \times treatment$,

where B is the coefficient of delta Cq, C is the coefficient of treatment, treatment is either 0 or 1 for placebo plus azacitidine or tamibarotene plus azacitidine.

Step 5: Using the probability level from Step 3 and the formula in Step 4, the optimal cutoff value of delta Cq can be calculated for each treatment arm.

Results from the logistic regression model, as well as a plot of the ROC curve, will be presented by treatment group for the mITT analysis set.

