8.6.2 Companion Diagnostic Assay Development

Blood samples collected at the Pre-screening Visit will be used for development of companion diagnostic assays for the RARA biomarker. Samples with residual material following completion of companion diagnostic assay development may also be used for exploratory research to evaluate MDS molecular features associated with response to drug treatment (Section 8.6.3).

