The primary endpoint will be tested at a full alpha level of 2.5%. To control the overall Type I error rate of the primary and key secondary endpoints, hierarchical testing will be performed in the following order: (1) primary endpoint; (2) key secondary endpoint. If hypothesis testing of the primary endpoint is rejected, the key secondary endpoint will be tested at the full alpha level of 2.5%; otherwise, the testing will be stopped. Secondary and exploratory efficacy endpoints will be tested using a two-sided, 5% significance level, and two-sided 95% CIs will be reported when appropriate, unless otherwise specified. P-values will be rounded to 4 decimal places. P-values less than 0.0001 will be displayed as "<0.0001"; p-values greater than 0.9999 will be displayed as ">0.9999".

When applicable, analyses will be stratified by IPSS-R risk group (Intermediate, High, and Very High Risk) and by geographical region (North America, Western Europe, plus Israel, and Eastern Europe).

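### The delta Cq cut-offs in SAP 7.4.6.8 come from a main-effects model, so they are prognostic for CR and do not show who gains more from tamibarotene on the odds-ratio scale; no cut-off method is given if an interaction is found

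*SAP*

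**What the plan says.** SAP 7.4.6.8 is one of the exploratory efficacy analyses and uses the mITT set. It models CR by logistic regression on treatment, delta Cq and their product, in order to "find the delta Cq cutoff value that optimally selects for the response from the receiver operating characteristic (ROC) curve".

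The sequence is fixed: "First, test if there is interaction between the treatment group and delta Cq by using the Wald Chi-Square test". The section gives no significance level for this test. The nearest general rule is in SAP 7.1.1: "Secondary and exploratory efficacy endpoints will be tested using a two-sided, 5% significance level".

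- **No interaction found:** the product term "will be removed from the model, and only treatment group and delta Cq will be kept in the model as covariates".
- **Interaction found:** "If there is an interaction, further investigation must be performed to qualitatively characterize the differences in RARA overexpression". Nothing further is specified.

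Five steps follow. The Step 1 code is "Model response (Event = '1') = delta_Cq treatment/ctable", with no product term. Steps 2 and 3 pick the probability level that maximises Youden's J. Step 4 writes the logit as an intercept plus B times delta Cq plus C times treatment. Step 5 solves this for a cut-off in each arm. The text does not expressly confine the steps to the no-interaction branch, but no other model is written.

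**The concern.** RARA status decides who may enter the trial (Protocol 5.1, criterion 2). A threshold described as best for this biomarker will naturally be read as a guide to who should receive tamibarotene. For that purpose one needs to know whether the tamibarotene-minus-placebo effect on CR changes with delta Cq.

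The plan gives numerical cut-offs only from a model in which the treatment odds ratio cannot change with delta Cq. Where delta Cq does appear to modify the effect, which is the informative case, it offers a qualitative description and no method. At stake is the interpretation of an exploratory output. No confirmatory test, alpha or eligibility rule is affected.

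**Working it through.** The SAP states no figure for this analysis, so there is none to reproduce. The check has two parts.

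**1. What the Step 4 model can show**

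Write logit(p) = a + B·x + C·t, with x = delta Cq and t = 1 for tamibarotene, 0 for placebo.

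- Treatment odds ratio at any x: exp(C). It does not depend on x.
- Cut-off at the chosen probability p*: [logit(p*) − a − C·t]/B.
- Placebo cut-off minus tamibarotene cut-off: C/B.

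The gap between the arm cut-offs is therefore the average treatment effect divided by the shared slope. It says nothing about a different biomarker effect by arm.

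Example with assumed values (CR at mean delta Cq 15% placebo and 34% tamibarotene; delta Cq in SD units, oriented so that higher x means higher CR; odds ratio per SD about 2, B = 0.69):

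- C = ln(0.34/0.66) − ln(0.15/0.85) = −0.663 + 1.735 = 1.071, and exp(C) = 2.92 at every x.
- Gap = 1.071/0.69 = 1.55 SD.
- The absolute CR difference still varies because baseline risk varies: 0.096 at −1.5 SD, 0.156 at −0.5, 0.222 at +0.5 and 0.260 at +1.5.

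Youden's J uses none of these differences. It sums the true-positive and true-negative percentages over both arms together and never compares the arms.

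**2. How informative a non-significant Wald test is**

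Inputs:

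- N = 190, from Protocol 9.4.2. The mITT size is redacted in SAP 7.2.1, so using 190 here is an assumption.
- 2:1 allocation gives 127:63.
- Two-sided 5% test, assumed from SAP 7.1.1.
- Design CR rates are redacted (Protocol 9.2, SAP 7.7), so they are assumed. As a plausibility check, the final critical difference of 0.1349 in SAP Table 16 gives SE = 0.1349/1.96 = 0.0688. Then p(1 − p) = 0.0688²/(1/127 + 1/63) = 0.1995, a pooled CR rate of about 27.5%. The pair 35%/14% pools to (127 × 0.35 + 63 × 0.14)/190 = 28.0%, and 34%/15% pools to 27.7%.

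Approximate power, with delta Cq standardised, true slope 0 on placebo and 0.8 on tamibarotene, CR 35% versus 14%:

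- Variance of the placebo slope ≈ 1/(63 × 0.14 × 0.86) = 0.132.
- Variance of the tamibarotene slope ≈ 1/(127 × 0.35 × 0.65) = 0.035.
- SE of the interaction ≈ √0.166 = 0.408, and 0.8/0.408 = 1.96, so power is about 50%.

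Simulations under these inputs put the proportion missing the interaction at 51% to 55%. The limit is the placebo arm, with only about 63 × 0.14 = 9 complete remissions.

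Results at 15% versus 34%, with 4,000 simulated trials per scenario:

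| Odds ratio per SD, placebo / tamibarotene | Interaction found | Passes to the main-effects cut-offs |
|---|---|---|
| 1.0 / 2.0 (predictive) | 37% | 63% |
| 1.0 / 1.5 (predictive) | 16% | 84% |
| 2.0 / 2.0 (prognostic only) | 5% | 95% |
| 1.0 / 1.0 (no relation) | 5% | 95% |

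The last two rows simply reflect the 5% level: the cut-off steps are reached about 95% of the time whenever there is no interaction, even if delta Cq has no relation to CR.

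**The case against.** The strongest reply is that the section sets out to select for response, not for differential benefit, and a Youden cut-off for CR answers that question. This is fair. It makes the issue one of labelling and usefulness, not an error against the stated aim.

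A second reply is that SAP 7.4.7.3 already plans the CR treatment effect by RARA-overexpression quartile, in a forest plot with 95% CIs. That also stands, so it would be wrong to infer that the SAP never examines benefit by RARA level. But the plot defines no cut-off, allows small subgroups to be skipped, and would have about 63/4 = 16 placebo patients per quartile. It does not correct the output of 7.4.6.8.

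Other stronger readings are also unsupported:

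- **That one cut-off is reported for both arms.** Step 5 gives one per arm. This does not rescue the method, since the gap is only C/B and an assay threshold has to be applied before treatment is chosen.
- **That a cut-off appears only when there truly is no interaction.** The condition is that none is found, which part 2 shows is different.
- **That the analysis can say nothing about benefit on any scale.** The limitation is on the odds-ratio scale. Absolute differences can vary with delta Cq, though the algorithm ignores them.
- **That the cut-off will feed the companion diagnostic.** Protocol 8.6.2 says "Blood samples collected at the Pre-screening Visit will be used for development of companion diagnostic assays for the RARA biomarker", but neither document links that work to this cut-off.

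**Conclusion.** The concern holds as a minor point. The algebra needs no assumption: cut-offs from the Step 4 model are prognostic for CR, differ between arms only by |C/B|, and cannot separate patients by relative benefit. That the interaction branch has no cut-off method is plain from the text; that the five steps belong to the other branch is an inference from the code and equation.

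The size of the detection problem depends on assumptions. With 190 patients, the assumed CR rates, a normally distributed standardised delta Cq and a 5% test, a real interaction of 0.8 per SD is missed in roughly half of trials, and weaker ones more often. The redacted design values could shift these percentages. How often a cut-off would fall within the observed delta Cq range depends on the grid of probability levels searched, so no figure is relied on for that.

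Severity is limited because the analysis is exploratory, its stated aim is response, and only RARA-positive patients are studied, so only thresholds within the enrolled range can be explored.

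**What to change.** Amend SAP 7.4.6.8 as follows:

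1. Keep the treatment-by-delta Cq term whatever the Wald test shows, and report its estimate with a 95% CI.
2. Report the model-based CR difference (tamibarotene minus placebo) with 95% CI across the enrolled delta Cq range.
3. Judge any candidate cut-off, common to both arms, by the CR difference above versus below it, with bootstrap intervals.
4. If the Youden step is kept, label its output as prognostic for CR only and not for patient selection.

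This also replaces the open-ended further investigation with a specified method for the interaction case. The cost is some SAP wording and a few lines of code. The downside is that an effect curve with wide intervals replaces a single number, which is a fair picture of what about 190 patients can show.

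### The delta Cq cut-off steps in SAP 7.4.6.8 put effect-coded SAS coefficients into a 0/1 formula, so the value labelled tamibarotene is the placebo cut-off and the value labelled placebo belongs to neither arm

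*SAP*

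**What the plan says.** SAP 7.4.6.8 sits among the exploratory efficacy methods and uses the mITT set. It models CR on treatment, delta Cq and their interaction, and drops the interaction if the Wald test does not find one. If one is found: "If there is an interaction, further investigation must be performed to qualitatively characterize the differences in RARA overexpression".

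Five steps then lead to a cut-off:

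- **Step 1** prints SAS code. The class statement is "Class treatment", with no PARAM= or REF= option. The model statement is "Model response (Event = '1') = delta_Cq treatment/ctable", so it has main effects only.
- **Steps 2 and 3** compute Youden's J from the classification table: "Obtain the Max (J) and find the corresponding probability level". This gives one level for the pooled data.
- **Step 4** says: "Use the fitted logit equation from SAS output". The logit is written as intercept plus B times delta Cq plus C times treatment, "where B is the coefficient of delta Cq, C is the coefficient of treatment, treatment is either 0 or 1 for placebo plus azacitidine" and tamibarotene plus azacitidine respectively.
- **Step 5** solves that equation at the Step 3 level, so that "the optimal cutoff value of delta Cq can be calculated for each treatment arm".

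Neither document states how SAS is to code the class variable.

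**The concern.** Step 4 is valid only if C was fitted with treatment coded 0/1. A bare class statement in PROC LOGISTIC does not do that. Its default is effect coding with the last sorted level as reference. With the SAP's own levels, placebo (0) becomes +1 and tamibarotene (1) becomes -1. C then has the opposite sign and half the size that the formula assumes, and the intercept has moved as well.

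Two things are at stake. First, a pre-specified recipe, followed as printed, labels the placebo cut-off as the tamibarotene one. Second, even with matching codes, one pooled probability level is solved in both arms with a common slope. The two cut-offs must then differ whenever the drug changes the CR rate, and a reader could take that gap for a difference in how RARA expression works in the two arms.

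**Working it through.** The SAP gives no numerical cut-off, so there is no figure to reproduce. The check is algebra, followed by fits to simulated data.

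**Inputs.** From the documents: the code and formula in SAP 7.4.6.8; 2:1 allocation (SAP 6.1); 190 patients (Protocol 9.4.2); the minimum critical CR difference of 0.1349 (SAP Table 16). Assumed, because the documents redact or omit them: CR rates, the delta Cq slope B (negative here), and normal delta Cq with SD 1. The SAS default is software behaviour, not something the documents state.

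**Algebra.** Let the 0/1 fit be a + B·x + c·treatment, and let L = logit(p*), where p* is the Step 3 level.

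- Correct cut-offs: placebo (L - a)/B; tamibarotene (L - a - c)/B.
- Under effect coding the same fit has intercept a + c/2 and C = -c/2.
- Step 4 with treatment = 1: (L - (a + c/2) + c/2)/B = (L - a)/B. This is the correct **placebo** cut-off.
- Step 4 with treatment = 0: (L - a - c/2)/B. This is the **midpoint** of the two correct cut-offs.
- Size of error: |c|/|B| for the value labelled tamibarotene, |c|/(2|B|) for the value labelled placebo.

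Predicted probabilities, J and p* do not depend on the coding. Nor does the Wald test of the interaction. Only the back-calculation fails.

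**One worked trial.** N = 190, assumed CR 20% vs 40%, true slope -1.0. The 0/1 fit gave a = -1.119, B = -0.903, c = 1.126. The effect-coded fit gave intercept -0.556 and C = -0.563. The level was p* = 0.48, so L = ln(0.48/0.52) = -0.080.

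| Label | Correct | SAP as written |
|---|---|---|
| Placebo | (-0.080 + 1.119)/(-0.903) = -1.15 | (-0.080 + 0.556)/(-0.903) = -0.53 |
| Tamibarotene | (-0.080 + 1.119 - 1.126)/(-0.903) = 0.10 | (-0.080 + 0.556 + 0.563)/(-0.903) = -1.15 |

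The gap between arms (tamibarotene minus placebo) is 1.25 when correct and -0.62 as written: halved, with the sign reversed. In 300 simulated trials (CR 20% vs 40%, slope -0.8) both identities held to rounding error, about 4e-16.

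**Size at the critical difference.** Take a control CR of 20% (assumed) and 20% + 13.5 points = 33.5%. Then c = ln(0.335/0.665) - ln(0.20/0.80) = 0.70.

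| B per SD | Tamibarotene error, 0.70/abs(B) | Placebo error, 0.35/abs(B) |
|---|---|---|
| -0.3 | 2.3 SD | 1.2 SD |
| -0.6 | 1.2 SD | 0.6 SD |

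Simulated median tamibarotene errors were also 2.3 and 1.2 SD.

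**Gap by construction.** With matching codes, tamibarotene minus placebo = (L - a - c)/B - (L - a)/B = -c/B. Nothing about the marker within an arm enters except the common slope. Large samples (N = 200,000) with the same delta Cq effect in both arms (slope -0.8) gave:

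| Assumed CR, placebo vs tamibarotene | Placebo | Tamibarotene | Gap |
|---|---|---|---|
| 20% vs 40% | -1.009 | 0.217 | 1.226 SD |
| 17% vs 30.5% | -0.798 | 0.151 | 0.950 SD |
| 25% vs 25% | -0.192 | -0.199 | -0.007 SD |

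In the first two rows, Youden cut-offs taken directly on delta Cq within each arm were close together: -0.25 and -0.07. When B is near zero the gap is unstable. In one N = 190 trial with fitted B = 0.048 and c = 1.225 it was -25 SD.

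**The case against.** The best defence is that the code is a template, that a careful programmer would see the +1/-1 design values in the output, and that the analysis only explores cut-offs. The swap also needs tamibarotene to sort last. The SAP's 0/1 levels give that. If tamibarotene sorted first, its cut-off would be right and the placebo one would still be the midpoint. All this limits the consequences, but it does not make the printed steps correct.

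On the gap between arms, the SAP may reasonably define its target as one predicted CR probability and solve for it in each arm. The gap then follows from that definition. It needs a caution and is not an error.

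A reader might infer more than the documents support:

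- **That no cut-off is produced when RARA level predicts benefit.** The SAP calls for further investigation in that case and does not say that a cut-off is withheld. The printed model fits the no-interaction case, so the other branch is under-specified, no more.
- **That this is the trial's only look at RARA level.** SAP 7.4.7.3 also plans CR effects by quartile of RARA overexpression, and SAP 7.4.6.5 leaves further expression-marker analyses to a separate document.
- **That the wrong value would pass into the companion diagnostic.** Protocol 8.6.2 assigns pre-screening blood to assay development. It does not say that this cut-off is used there.

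**Conclusion.** SAP 7.4.6.8 is wrong as written. Given PROC LOGISTIC's default coding and the SAP's 0/1 levels, the cut-off labelled tamibarotene is exactly the placebo one, and the cut-off labelled placebo is the midpoint of the arms. This is algebra and does not depend on the assumed rates. The size does: 1.2 to 2.3 SD of delta Cq for tamibarotene at CR 20% vs 33.5% and B from -0.6 to -0.3. Every enrolled patient is RARA-positive, so the real spread of delta Cq is restricted and these figures are illustrative.

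Even after correction, the gap between the arms' cut-offs is |c/B| and reflects the treatment effect. The matter is confined to one exploratory analysis. Primary CR and key secondary OS testing are untouched.

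**What to change.** 1. In Step 1 write `class treatment (ref='0') / param=ref;` so that the output coefficients fit the 0/1 formula. Alternatively keep the code and state in Step 4 that placebo is entered as +1 and tamibarotene as -1.
2. Add one sentence to Step 5: the two cut-offs come from one pooled probability level and a common slope, differ by |C/B| (C on 0/1 coding) by construction, and their difference is not evidence that the biomarker acts differently in the two arms.

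The cost is one line of code and one sentence, with no new data and no change to any other analysis.

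One tempting replacement should be avoided: choosing the cut-off from tamibarotene outcomes and then comparing the arms above and below it in the same patients. With 127 vs 63 patients, CR 33.5% vs 20% and a delta Cq unrelated to response, simulations gave a spurious average difference of about 13 to 18 points between the two subgroups' treatment effects. The value depended on the direction rule and the minimum subgroup size.
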